4.2.4. Total Daily Steps

Baseline TDS is the average number of daily steps a patient completes, computed using the daily steps recorded during the first 14 days of study participation (study day 1 through study day 14). The average will be calculated as the sum of the daily TDS divided by the number of days with nonmissing TDS. If no step data are available for study day 1 through study day 14, the ‘baseline TDS’ is the first available TDS after study day 14.

Baseline TDS are computed for those patients in the ankle accelerometry analysis set.

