4.2.3. Inhalational Flow Values

The baseline inspiratory flow values are computed using the set of inhalations taken by the patient during study day 1 through day 14. Among these inhalations, the inhalation with the highest maximal inhalation flow (MIF) value is considered the ‘baseline inhalation’. The baseline MIF, inhalational volume, inhalation duration, and time to MIF values are those of the identified ‘baseline inhalation’. If no inhalations were taken during study day 1 through study day 14, the ‘baseline inhalation’ is the first available inhalation after study day 14.

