4.5. Study Day and Study Week

Study days will be numbered relative to the earliest date an ABS eMDPI device was dispensed (ie, ... -2, -1, 1, 2, ...). Day 1 is defined as the earliest date an ABS eMDPI device was dispensed and Day -1 is the day before the first ABS eMDPI device was dispensed.

Week I is defined as study day $(j + 1)$ to study day $(j + 7)$, inclusive where $I = 1$ to 12 and $j = 0, 7, 14, 21, 28, 35, 42, 49, 56, 63, 70, 77, 84$, respectively.

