7.2.2.2. Actual and Change from Baseline in Week *Y* Inhalational Flow Values

Summary descriptive statistics of the actual inhalational flow values and change from baseline in MIF, inhalational volume, inhalation duration, and time to MIF for each study week (1 through 12) will be presented overall, and by CAE status and by CAE severity.

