7.3.2.2. Actual and Change from Baseline in Week *Y* Total Daily Steps

Summary descriptive statistics of the actual Week *Y* TDS and change from baseline in TDS for each study week (1 through 12) will be presented overall, and by CAE status and by CAE severity (Yes: severe, moderate; No) using the ankle accelerometry analysis set.

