7.4.2.2. Actual and Change from Baseline in Week Y Sleep Disruption Indices

Summary descriptive statistics of the absolute Week Y nighttime average sleep latency time, longest nighttime wake episode, total time awake at night, and SDI composite score and change from baseline in these four sleep disruption indices for each study week (1 through 12) will be presented overall, and by CAE status and by CAE severity.

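### Change from baseline is tabulated for Weeks 1 and 2, which make up the Day 1–14 baseline window, so those entries for steps, two sleep measures and flow are constrained by construction

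*SAP*

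**What the plan says.** **Baseline.** SAP 4.2.4 takes baseline steps as a mean "computed using the daily steps recorded during the first 14 days of study participation (study day 1 through study day 14"). On missing days it says: "The average will be calculated as the sum of the daily TDS divided by the number of days with nonmissing TDS". SAP 4.2.5 treats each sleep parameter in the same way. SAP 4.2.3 says that baseline flow is "computed using the set of inhalations taken by the patient during study day 1 through day 14". The inhalation with the highest MIF in that set supplies all four baseline flow values.

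**Fallback.** When a patient's 14-day window holds no steps at all, SAP 4.2.4 uses the earliest later value instead. Sleep and flow have similar fallbacks.

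**Weeks.** SAP 4.5: "Week I is defined as study day $(j + 1)$ to study day $(j + 7)$, inclusive". With j = 0 and j = 7, Week 1 is Days 1–7 and Week 2 is Days 8–14.

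**Weekly values.** Steps (7.3.1), sleep latency and total time awake (7.4.1) are means over the non-missing days of the week. The longest nighttime wake episode is the largest value in the week, and the SDI composite adds it to the other two (7.4.1). Weekly flow values come from the inhalation with the highest MIF in the week (7.2.1).

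**Tables.** Besides actual values, the SAP asks for:
- 7.2.2.2: "change from baseline in MIF, inhalational volume, inhalation duration, and time to MIF for each study week (1 through 12")
- 7.3.2.2: "change from baseline in TDS for each study week (1 through 12")
- 7.4.2.2: "change from baseline in these four sleep disruption indices for each study week (1 through 12")

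All three are given overall, by CAE status and by CAE severity. None leaves out Weeks 1 and 2.

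**The concern.** A reader takes change from baseline as movement away from an earlier state. In the Week 1 and Week 2 columns there is no earlier state, because the baseline is built from those two weeks. A patient who worsens in Week 2 lowers his or her own baseline and so appears better than baseline in Week 1.

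The study asks how these signals move around exacerbations, and the tables are split by CAE status and severity. Two of the twelve change columns would give a distorted position relative to zero, and the spread would jump at Week 3 with no clinical cause. The flow table is affected in the whole ITT set (SAP 7). The step and sleep tables come from the two accelerometry subsets, planned at 100 patients each.

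**Working it through.** The documents give no figure to reproduce here, so the check is algebra on the SAP's definitions. They also give no step values or variances. The step levels and the daily SD of 2000 below are assumptions. The SD ratios do not depend on that 2000.

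**1. Steps, sleep latency, total time awake**

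Let W1 and W2 be the weekly means and n1 and n2 the non-missing days. Then

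- B = (n1·W1 + n2·W2)/(n1 + n2)
- W1 − B = n2(W1 − W2)/(n1 + n2)
- W2 − B = −n1(W1 − W2)/(n1 + n2)
- n1(W1 − B) + n2(W2 − B) = 0

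For W1 = 6000 and W2 = 5000 steps/day, a true fall of 1000:

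| n1, n2 | Baseline | Week 1 change | Week 2 change |
|---|---|---|---|
| 7, 7 | 5500 | +500 | −500 |
| 7, 3 | 5700 | +300 | −700 |
| 3, 7 | 5300 | +700 | −300 |
| 7, 1 | 5875 | +125 | −875 |

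Equal days give exact mirror images at half size. Unequal days give a different split, and only the day-weighted sum is zero.

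**2. Spread, complete data, no true change**

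With independent days of variance s²:

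- Weeks 1–2: Var = s²(1/7 − 1/14) = s²/14
- Week 3 on: Var = s²(1/7 + 1/14) = 3s²/14
- SD ratio = 1/√3 = 0.577

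For s = 2000:

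| Day-to-day correlation | SD, Weeks 1–2 | SD, Week 3 on | Ratio |
|---|---|---|---|
| None | 535 | 926 | 58% |
| Exchangeable, 0.3 | 447 | 775 | 58% |
| AR(1), 0.3 | 675 | 1190 (Week 3), 1211 (later) | 57%, 56% |

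Exchangeable correlation multiplies both variances by 1 − 0.3 = 0.7, so the ratio does not move.

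**3. Flow**

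Baseline and weekly inhalations are picked by the same rule, highest MIF. The highest in Days 1–14 is also the highest in the week in which it falls. In that week the baseline and weekly inhalations are the same one, so all four changes are 0 (barring ties). In the other week the highest MIF cannot exceed the 14-day highest, so the MIF change is at most 0. A simulation with one independent value per day and no true change gave a zero change in about 50% of patients in each of Weeks 1 and 2 and a positive MIF change in none. In Week 3 about 33% were positive.

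**4. Longest nighttime wake episode and SDI composite**

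Here a weekly maximum is set against a 14-day mean. With complete data the two changes of the wake episode sum to (max1 − mean1) + (max2 − mean2), which is never below zero. For independent nights with an assumed mean of 20 minutes and no true change, the average change in simulation was +6.8 minutes in Weeks 1, 2, 3 and 12 (normal, SD 5), or +15.4 to +15.5 (lognormal, SD 10). The composite contains this maximum, so it does not cancel either.

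**The case against.** The strongest defence is that subtracting one constant per patient preserves every week-to-week difference. Going from +500 to −500 still shows the full 1000-step fall, and the actual weekly values stand in the same summaries. This is right. The harm is confined to position relative to zero and to the spread in two columns.

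Three stronger inferences are tempting, and the documents do not support them:

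- *All the sleep changes cancel.* SAP 7.4.2.2 tabulates four indices, and the algebra covers two. The longest wake episode and the composite are shifted upward instead.
- *A Week 2 change is always shown at half size.* That needs equal numbers of non-missing days. A patient with no data on Days 1–14 has no Week 1 or Week 2 change, because the fallback baseline lies later.
- *The two columns say nothing about patients.* For the mean-based measures each entry is a scaled Week 1 versus Week 2 contrast from that patient's data. It carries information under a misleading label.

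It is also true that no inference rests on these tables. The test in SAP 7.1.2.3 and the comparisons in 7.5.2.1 set two pre-exacerbation weeks against each other and do not use these baselines. The sample size in SAP 2.3 does not use them either. That limits the weight of the point but does not make the entries correct.

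**Conclusion.** The point holds as a minor presentation fault. For steps, sleep latency and total time awake, the day-weighted sum of each patient's Week 1 and Week 2 changes is zero, whatever the CAE status. With equal days a Week 2 fall is halved and mirrored as a Week 1 rise. The SD of change is 58% of its later value under independent or exchangeable days and about 56–57% under AR(1) correlation of 0.3, assuming complete data and constant variance. For flow, one of the two weeks is zero on all four measures, barring ties, for any patient with use on Days 1–14, and the MIF change in the other week can only be zero or negative. No test, sample size or primary conclusion is affected.

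**What to change.** In SAP 7.2.2.2, 7.3.2.2 and 7.4.2.2, state that actual values are presented for Weeks 1–12 and change from baseline for Weeks 3–12 only, because Weeks 1 and 2 form the baseline window.

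The cost is one sentence per section and two fewer change columns in each of three tables, with no new data. There is a small loss: the within-patient contrast of Week 1 with Week 2, which the dropped columns carry at reduced scale, is no longer shown.

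The change leaves two separate mismatches in place from Week 3 on. A weekly maximum is still compared with a mean baseline for the longest wake episode and the composite. For flow, a 7-day best inhalation is still compared with a 14-day best.

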4.2.5. Sleep Parameters

There are 8 measures of sleep disruption: (i) nighttime average total time in bed, (ii) nighttime average total sleep time, (iii) nighttime average sleep latency time, (iv) nighttime average wakening after sleep onset, (v) total time awake at night, (vi) daytime average minutes asleep, (vii) longest daytime sleep episode and (viii) longest nighttime wake episode. The first 7 sleep parameters are provided via Philips accelerometry and longest nighttime wake episode is derived from the accelerometry data as follows:

The sleep interval data provided via Philips accelerometry includes the activity state ("sleep"/"awake") every 30 seconds during the sleep interval. The number of successive 30 second "awake" states occurring between "sleep" states within the sleep interval is summed to determine the duration of a given "awake" state. The longest nighttime wake episode is the summated "awake" state with the longest duration during the sleep interval.

The baseline value of a given sleep parameter (eg, nighttime average total time in bed) is the average sleep parameter (eg, nighttime average total time in bed), computed using the sleep parameter (eg, nighttime average total time in bed) values captured by accelerometry during study day 1 through day 14. The average will be calculated as the sum of the average sleep parameter divided by the number of days with nonmissing values of the average sleep parameter. If no sleep parameter data are available for study day 1 through study day 14, the 'baseline value of a given sleep parameter' is the first available valid sleep parameter value after study day 14.

Baseline sleep parameters are computed for those patients in the wrist accelerometry analysis set.

4.3. Time on Study

Time on study is the number of days from date of informed consent to date of completion or last contact date plus 1.

4.4. eMDPI Time on Study

The eMDPI time on study is the number of days (D_{emdpi}) from the last device return date to the date the first ABS eMDPI device was dispensed. For instances where the last device return date is missing the patient's last date of contact or study completion date will be used, whichever comes first.

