7.1.2. Analysis Methods for Albuterol Use

7.1.2.1. Pattern of Baseline Daily and Weekly Albuterol Use

Summary statistics including 95% CIs of the proportion of eMDPI time on study days when a patient took 0 to 4 inhalations a day (number of days a given patient took 0 to 4 inhalations a day divided by the total number of eMDPI study days for a given patient) will be summarized overall and by CAE status and by CAE severity. In addition, the proportion of patients exhibiting

weekly baseline albuterol use (Week 1, Week 2, ..., Week 12) will be summarized overall and by CAE status and by CAE severity.

Week 1 and Week 2 patient albuterol use patterns, “WK1:I#iD#dMT4Y/N” and “WK2:I#iD#dMT4Y/N” designation, will be summarized descriptively (counts and percent) overall and by CAE status and by CAE severity.

7.1.2.2. Total Number of Inhalations in the Days Preceding the Peak of a CAE

For patients who experienced a CAE, summary descriptive statistics of the total number of inhalations taken in 1 day (eg, the 24-hour period on the day prior to the date of the CAE symptom peak) and at 3, 5, 7, 10, 14, and 21 days preceding the date of the CAE symptom peak will be presented overall and by moderate CAEs and severe CAEs.

In this analysis, among patients experiencing more than 1 CAE, the subsequent CAEs can be considered a separate CAE distinct from the first (preceding) CAE provided the patient exhibited at least 1 day of baseline albuterol use after the first (preceding) CAE’s date of symptom peak and prior to the subsequent CAE’s date of symptom peak. For patients who experience multiple CAEs (eg, 3), for a given number of days preceding a CAE (eg, 21 days), if the (eg, third) CAE overlaps with the time period of the preceding (eg, second) CAE, the CAE (eg, third CAE) should not be included in the analysis.

Mean and 95% CI of the total number of inhalations per day for each eMDPI study day will be summarized graphically. The number of patients contributing to the summary statistic at study at Day 7, 14, 21, 28, 35, 42, 49, 56, 63, 70, 77, and 84 will also be presented. Three line graphs will be presented in 1 figure: “Overall” and by “CAE Status” (Yes, No). Three line graphs will be presented in a second figure; “CAE Status No”, “CAE Status Yes: Severe” and “CAE Status Yes: Moderate”.

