Among patients who did not experience a CAE, summary statistics, including 95% CIs, of the proportion of eMDPI time on study days when a patient exceeded a given threshold of albuterol use (number of days a given patient's single day's albuterol use exceeded 4 inhalations / total number of eMDPI study days for a given patient) will be summarized for 3 thresholds defining an increase in albuterol use;

- (i) a single day's albuterol use exceeding 4 inhalations;
- (ii) a single day's albuterol use exceeding 12 inhalations;
- (iii) a single day's albuterol use exceeding 20 inhalations.

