10.2. Duration of Exposure to IMP

Duration of exposure to IMP (days and weeks) for the individual patient is the number of days the patient took at least 1 inhalation from the ABS eMDPI. Patients receive the ABS eMDPI devices at Baseline and subsequently by courier on Day 21. Duration of exposure is determined from all eMDPIs used by a patient and it is the total number of unique dates recorded by the eMDPIs from the dispense date and return date of a given device, inclusive. Note, if a patient uses more than 1 eMDPI device on a given day, it is still only 1 day of exposure for that given day. The patient's last date of contact or study completion date will be used as the device return date if the device return date is missing.

Duration of exposure (days and weeks) will be summarized using descriptive statistics overall, and by CAE status and by CAE severity.

Exposure to IMP, expressed in mcg units, will also be summarized using descriptive statistics. Average daily exposure, average weekly exposure, and the maximum exposure in a single day will be summarized overall, and by CAE status and CAE severity. One inhalation recorded by the ABS eMDPI is equivalent to 90 mcg.

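### SAP 4.4 makes the eMDPI day denominator one day short of the study-day count, so day proportions can exceed 100%; separately, part-day steps on Day 1 can enter the step baseline as a full day

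*SAP*

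**What the plan says.** **Day counts.** SAP 4.4 sets eMDPI time on study to the number of days "from the last device return date to the date the first ABS eMDPI device was dispensed". SAP 4.3, directly above it, states the extra day: "Time on study is the number of days from date of informed consent to date of completion or last contact date plus 1". The time-to-CAE definition in SAP 7.5.1 also adds 1. SAP 4.5 fixes the numbering: "Day 1 is defined as the earliest date an ABS eMDPI device was dispensed".

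**Proportions.** SAP 7.1.2.1 summarises, for each patient, the "number of days a given patient took 0 to 4 inhalations a day divided by the total number of eMDPI study days". SAP 7.1.2.4 does the same for use above 4, 12 and 20 inhalations in patients without a CAE, for example "number of days a given patient's single day's albuterol use exceeded 4 inhalations / total number of eMDPI study days for a given patient". Both sections describe these as proportions of eMDPI time-on-study days. Neither gives the first and last day of the numerator.

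**Steps.** SAP 4.2.4 says baseline TDS is "computed using the daily steps recorded during the first 14 days of study participation (study day 1 through study day 14", divided by the number of days with a nonmissing value. SAP 7.3.1 uses the same divisor for weekly TDS, and Week 1 is Days 1 to 7. SAP Table 1 has accelerometers dispensed at visit 2, which is Day 1. There is no wear-time or partial-day rule.

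**The concern.** Return date minus dispensing date gives one day fewer than the number of study days from dispensing to return when dispensing is Day 1. If the numerator counts days by their study-day number and the denominator is that difference, the two do not match. A proportion can pass 100%, and the share of days at or below 4 inhalations plus the share above 4 can total more than 1. These proportions are reported with summary statistics and 95% CIs, so an impossible value would be visible in the output.

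The step issue is separate. A device handed over during a clinic visit cannot record steps taken earlier that day. If the Day 1 record is nonmissing, the only filter lets it through as a whole day. TDS is collected as a marker of exertional dyspnea (Protocol 2.1.1) and is summarised as change from baseline before a CAE (SAP 7.3.2.1), so an error in the baseline carries into every change value.

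**Working it through.** The plan states no figure for either point, so there is nothing to reproduce first.

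**A. Denominator**

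Inputs: dispensing on Day 1 (SAP 4.5); return on study day n; denominator as in SAP 4.4; final visit on Day 84 ±14 (SAP Table 1), so completers return from Day 70 to Day 98.

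- Denominator under 4.4: D = n − 1.
- Study days from Day 1 to the return date inclusive: n.
- With k days at or below 4 inhalations, the proportion is k/(n − 1). It exceeds 1 only when k = n, that is, when the patient meets the criterion on every day. Its largest value is n/(n − 1).
- For any patient, the two complementary proportions sum to k/(n − 1) + (n − k)/(n − 1) = n/(n − 1), which is above 1.

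| Return day n | D under 4.4 | Largest proportion |
|---|---|---|
| 98 | 97 | 101.0% |
| 84 | 83 | 101.2% |
| 70 | 69 | 101.4% |
| 29 | 28 | 103.6% |
| 15 | 14 | 107.1% |
| 8 | 7 | 114.3% |
| 1 | 0 | undefined |

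Early leavers are in the analysis: SAP 3.1 and 7 use all enrolled patients for the endpoints, and SAP 2.3 expects 10% dropout (400 × 0.10 = 40 patients). With 'plus 1', D = n and the maximum is 100% in every row.

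**B. Step baseline**

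Assumption: a share f of Day 1's steps is captured. The documents give no dispensing time, so f is shown over its whole range. Take the patient's true daily level as constant and equal to 1.

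- Baseline with 14 nonmissing days: (13 + f)/14, low by (1 − f)/14.
- Week 1 mean with 7 nonmissing days: (6 + f)/7.
- Change on a full later day, or in a week of full days: 1 − (13 + f)/14 = +(1 − f)/14. The true change is 0.
- Week 1 change: (6 + f)/7 − (13 + f)/14 = −(1 − f)/14.

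| f | Baseline error | Change, full later days | Change, Week 1 |
|---|---|---|---|
| 0 | −7.1% | +7.1% | −7.1% |
| 0.25 | −5.4% | +5.4% | −5.4% |
| 0.5 | −3.6% | +3.6% | −3.6% |
| 0.75 | −1.8% | +1.8% | −1.8% |
| 1 | 0 | 0 | 0 |

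If the device is returned on Day 84 and that day is equally incomplete, the Week 12 change has the same downward error as Week 1. With m nonmissing baseline days including Day 1, the baseline is low by (1 − f)/m; for m = 7 and f = 0.5 that is 7.1%.

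**The case against.** **The denominator can be read another way.** The formulas in 7.1.2.1 and 7.1.2.4 refer to eMDPI study days, not to the quantity defined in 4.4 by its symbol. In 7.1.2.2 the same term is used for numbered days, with patient counts shown at Day 7 through Day 84. Read that way, a Day 84 return has a denominator of 84 and nothing exceeds 100%. This is a fair reading, but the sentences in 7.1.2.1 and 7.1.2.4 also speak of eMDPI time-on-study days, which leads back to 4.4. At best the text is ambiguous, and the repair is one phrase.

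**The effect is small.** For a Day 84 return the excess is at most about 1.2%, in a descriptive summary. That stands. Larger values need early departure.

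**The step error does little harm.** SAP 7.3.2.1 reports actual TDS beside change from baseline. A low baseline shifts all of a patient's later changes by one constant, so the fall across the pre-CAE days is unaltered, provided none of them is a partial day. Day 1 enters the baseline whether or not the patient has a CAE, and nothing in the documents suggests that capture differs by CAE status. The ankle subset is planned at 100, so at the 20% to 25% CAE rate in SAP 2.3 about 20 to 25 patients contribute. All of this stands and limits the consequence. It does not make the baseline right.

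**Stronger readings that the documents do not support.** A reader might infer that all step changes are biased upward; Week 1 is biased downward, and the week holding the return day can be too. A reader might also take the exposure duration in SAP 10.2, the "it is the total number of unique dates recorded by the eMDPIs from the dispense date and return date of a given device, inclusive", as a numerator over 4.4. It shows inclusive date counting elsewhere in the plan, but it is never divided by eMDPI time on study.

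**Conclusion.** Both points hold within limits.

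On the plain reading of SAP 4.4, the denominator is one day short of the inclusive count. The largest proportion is 101.2% for return on Day 84, 107.1% for Day 15, and undefined for a same-day return. This rests on the numerator running from Day 1 to the return date, which 4.5 suggests but 7.1.2.1 and 7.1.2.4 do not state. The error is slight for completers and larger for early leavers.

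The step point is conditional on Day 1 having a nonmissing, incomplete record. The plan does nothing to exclude one, but its frequency and the share captured are unknown. With 14 nonmissing days the baseline is low by 0% to 7.1%. Change from baseline is then too high on full later days and in weeks without a partial day, and too low in Week 1. Actual TDS on full days is not affected.

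It would go too far to conclude that the pre-CAE decline in steps is hidden, or that the excess proportions fall mainly in patients without a CAE. The within-patient decline survives a constant shift, and the documents do not show how low use divides by CAE status.

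**What to change.** 1. In SAP 4.4, add 'plus 1' to the definition. In 7.1.2.1 and 7.1.2.4, state that the numerator runs from Day 1 to the return date inclusive (or to the substitute date that 4.4 gives when the return date is missing), and that the denominator is the 4.4 quantity. The summary in 5.10 then follows the same count.
2. In SAP 4.2.4 and the matching rule in 4.6, compute baseline TDS from Days 2 to 14, keeping the fallback to the first available value after Day 14.
3. In SAP 7.3.1, leave the dispensing day and the return day out of the weekly TDS means. Keep the week definitions in 4.5.
4. Leave the albuterol measures unchanged. Dropping Day 1 from them as well would make the Week 1 use pattern six days against seven in Week 2, and could remove threshold or landmark events on Day 1. The denominator error does not require it.

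The cost is SAP wording and derivation code, with no new data collection. The downside is that one or two days of step data per patient are not used.

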APPENDIX F. LOST TO FOLLOW-UP

A patient will be considered lost to follow-up if he/she repeatedly fails to return for scheduled visits and is unable to be contacted by the investigational center.

The following actions must be taken if a patient fails to return to the investigational center for a required study visit:

- The investigational center must attempt to contact the patient and reschedule the missed visit as soon as possible and counsel the patient on the importance of maintaining the assigned visit schedule and ascertain whether or not the patient wishes to and/or should continue in the study.
- In cases in which the patient is deemed lost to follow-up, the investigator or designee must make every effort to regain contact with the patient (where possible, 3 telephone calls and, if necessary, a certified letter to the patient's last known mailing address or local equivalent methods). These contact attempts should be documented in the patient's medical record.
- Should the patient continue to be unreachable, he/she will be considered to have withdrawn from the study with a primary reason of "lost to follow-up."

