4.6. Handling Withdrawals and Missing Data

Any data that was collected prior a patient's withdrawal from the study will be used for analysis and presented in the data listings.

The following imputation rules will be used;

- If the return date of the last ABS eMDPI device returned is missing the patient's last date of contact or study completion date will be used as the return date (see Section 4.4 and Section 10.2).
- Adverse events or serious adverse events with missing start dates will be considered treatment emergent (see Section 10.4).
- If a patient never used the ABS eMDPI during the study or download of a given ABS eMDPI device was not successful, study day and weekly inhalational flow values will be missing. If download of a given wrist or ankle accelerometer was not successful, TDS and SDI indices will be missing. These missing data will not be imputed.
- In the derivation of Study Day X Inhalation flow values, if there was no albuterol use on Study Day X , then the closest preceding nonmissing Study Day Inhalation' is used as the 'Study Day X Inhalation' and the inhalational flow values for Study Day X are assigned accordingly (see Section 7.2.1).
- For patients in the ankle accelerometry analysis set if no step data are available for study day 1 through study day 14, the 'baseline TDS' is the first available TDS after study day 14 (see Section 4.2.4).
- For patients in the wrist accelerometry analysis set if no sleep parameter data are available for study day 1 through study day 14, the 'baseline value of a given sleep parameter' is the first available valid sleep parameter value after study day 14 (see Section 4.2.5).

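### eMDPI time on study is not capped at study exit, so an inhaler returned late adds off-study days to the descriptive albuterol-use summaries

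*SAP*

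**What the plan says.** SAP 4.4 counts eMDPI time on study "from the last device return date to the date the first ABS eMDPI device was dispensed". The study exit date enters only as a fallback: "For instances where the last device return date is missing the patient's last date of contact or study completion date will be used". The sentence then says which of the two dates applies: "last date of contact or study completion date will be used, whichever comes first". That closing phrase chooses between the two fallback dates. It does not compare either of them with a return date that was recorded. SAP 4.6 has the same trigger, "If the return date of the last ABS eMDPI device returned is missing", but does not say which of the two fallback dates prevails. Its sentence on withdrawals keeps data collected before withdrawal and says nothing about days after it.

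The resulting day count is used in several places:

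- SAP 7.1.2.1 takes the "number of days a given patient took 0 to 4 inhalations a day divided by the total number of eMDPI study days" and summarises it overall, by CAE status and by CAE severity.
- SAP 7.1.2.2 plots mean inhalations per day over each eMDPI study day.
- SAP 7.1.2.4 uses it as the denominator, in patients without a CAE, for the proportions of days above 4, above 12 ("a single day's albuterol use exceeding 12 inhalations") and above 20 inhalations.
- SAP 5.10 reports it directly.

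The planned return point is the last visit or early termination (Protocol 3.1 and 5.1; SAP 2.1), and Protocol 4.3 requires return on withdrawal.

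**The concern.** SAP 4.3 stops time on study at completion or last contact, while SAP 4.4 stops eMDPI time at device return. For a patient who leaves and sends the last inhaler back later, the two clocks separate. The days between are outside participation, and the requirement to use the study inhaler as the only rescue agent lasts only as long as participation. A day without a recorded inhalation then no longer shows that no rescue was needed.

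The 7.1.2.1 category includes zero, so an unused day after exit is a low-use day. The same day enlarges the 7.1.2.4 denominator without being able to add to its numerator, and it enters the daily graph as a zero. If the inhaler is used after exit, that use is counted as on-study use. Either way, the summary describes a period the study was not observing. A late returner who stopped using the device would look better controlled than the on-study record shows.

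**Working it through.** **Plan figures.** No stated sample size, event count or significance level depends on this definition. The one planning figure used is the 10% dropout, which reproduces: 400 × 0.10 = 40 dropouts, leaving 360.

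**Notation.** E = days on study; L = days from exit to last device return; p = on-study share of days with 0 to 4 inhalations. No use after exit is assumed. The documents give none of E, L or p, so all values below are assumptions. SAP 4.4 adds no extra day to its date difference; that one-day matter is ignored here.

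**Formulas.**

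- Reported low-use share: q = (pE + L)/(E + L).
- Share of days above a threshold, and the patient's mean daily use: each multiplied by E/(E + L).
- Shift in the cohort mean if all 40 dropouts return late and completers have no lag: (40/400) × (q − p).

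**Illustration: E = 30, p = 60%.**

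- L = 14: q = (18 + 14)/44 = 72.7%. Days above 4 inhalations: 40% × 30/44 = 27.3%.
- L = 30: q = (18 + 30)/60 = 80.0%. Days above 4 inhalations: 40% × 30/60 = 20.0%.
- Cohort shift: 0.10 × 12.7 = 1.3 points and 0.10 × 20.0 = 2.0 points.
- If only a quarter of the dropouts fit this pattern: about 0.3 to 0.5 points.

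**Other assumed values, L = 7, 14, 28, 56.**

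- E = 28, p = 50%: q = 60.0%, 66.7%, 75.0%, 83.3%.
- E = 84, p = 50%: q = 53.8%, 57.1%, 62.5%, 70.0%.
- E = 28, p = 80%: q runs from 84.0% (L = 7) to 93.3% (L = 56).
- Cohort mean with all 40 dropouts at E = 28: from 50.0% to 51.0–53.3%, or from 80.0% to 80.4–81.3%. The shift is 0.4 to 3.3 points.

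**Planned case.** L = 0 gives q = p, so there is no effect.

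**Analyses that do not use this clock.** The t-test in SAP 7.1.2.3 uses the 14 days before the CAE symptom peak. SAP 7.5.2.1 uses the 14 days before CAE onset and requires the patient to be on study and CAE-free for that time. The Kaplan-Meier analysis in 7.5.2.2 censors when follow-up ends. None of these moves.

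**The case against.** The main defence is that the gap should not arise. Inhalers are collected at Visit 5, which is also the early termination visit, and the documents describe no later return route. That visit also assesses exacerbations, so a delayed early termination visit would extend CAE inquiry to the same date. This stands: the frequency of late return is unknown and may be low. It does not settle the matter, because Protocol 4.3 asks for the early termination assessments only if possible, and SAP 4.4 takes the last return date, so one late inhaler is enough to extend the clock.

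It is also true that SAP 7.1.2.1 has no written rule that a day without a record is zero; the only explicit one is in 7.5.2.1, for on-study time. The inference is nevertheless hard to avoid where the category itself starts at zero.

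Four stronger readings are tempting and are not supported:

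- *Loss to follow-up in general inflates the counts.* Protocol Appendix F covers a patient who repeatedly "fails to return for scheduled visits and is unable to be contacted by the investigational center". Such a patient who never returns an inhaler has no return date, and the SAP 4.4 fallback already ends the clock.
- *The comparison of high-use days by CAE status is diluted.* There is no such comparison. The proportions in 7.1.2.4 are planned only for patients without a CAE; patients with a CAE get a different statistic, the days before the peak at first exceedance. Only the low-use share in 7.1.2.1 is shown by CAE status.
- *The bias favours the CAE-free group.* The documents do not say that late returners would be concentrated there.
- *The hypothesis tests are biased.* Their windows precede the CAE.

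**Conclusion.** The point holds as a defect in a definition with descriptive consequences. As written, SAP 4.4 and 4.6 give the wrong day base for any patient whose last recorded device return falls after study exit. For such a patient the distortion can be large: 60% becomes 73% or 80% in the illustration, assuming exit on Day 30, lags of 14 or 30 days and no use after exit.

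At cohort level, the 1 to 2 points is a ceiling for that illustration, since it assumes every one of the 10% dropouts returns that late. The wider grid of 0.4 to 3.3 points makes the same assumption about dropouts. With returns at the planned visit the effect is zero. No planned test or time-to-event analysis in the SAP changes. This is a minor point, worth correcting because the correction is short and the error is otherwise built into the denominator.

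**What to change.** In SAP 4.4, define the end of eMDPI observation for every patient as the earlier of the last device return date and the study completion or withdrawal date, whether or not the return date is missing. Put the same rule in 4.6. State that days after this end are unobserved, neither zero nor use, in 7.1.2.1, 7.1.2.2 and 7.1.2.4.

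Leave the exposure window in 10.2 as it is. Duration of exposure there counts only days with at least one recorded inhalation, so unused days cannot inflate it, and a cap would delete real, timestamped exposure from the safety summary.

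The cost is a phrase in two sections and a sentence on unobserved days, with no new data collection. The small downside is that device use recorded after study exit drops out of the albuterol-use summaries, although it stays in the exposure summary.
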